5.2.2. Part 2 Inclusion Criteria

1. In addition to inclusion criteria listed for Part 1, Part 2 will enroll **GCB-DLBCL, tFL and MM subjects only**.
 - Relapsed and/or refractory MM or tFL that have failed prior standard therapy and for which there is no standard salvage regimen
2. Lymphoma subjects will be required to undergo EZH2 mutation testing. This will require availability of archival tissue, or willingness to undergo fresh biopsy, for central testing of EZH2 mutation status.
3. Based on the results of the mutation test, lymphoma subjects may be enrolled in one of four cohorts:
 - GCB-DLBCL EZH2 mutant cohort:
 - Tumors must contain one, or more, of the following EZH2 activating mutations: Y641F; Y641N; Y641S; Y641H; Y641C; A677G; and/or A687V
 - GCB-DLBCL EZH2 wild type cohort:
 - Tumors that do not contain one of the above mutations
 - Subjects with tumors harboring EZH2 mutations other than the seven outlined above will be enrolled in the EZH2 wild type cohort
 - tFL EZH2 mutant cohort:
 - Tumors must contain one, or more, of the following EZH2 activating mutations: Y641F; Y641N; Y641S; Y641H; Y641C; A677G; and/or A687V
 - tFL EZH2 wild type cohort:
 - Tumors that do not contain one of the above mutations
 - Subjects with tumors harboring EZH2 mutations other than the seven outlined above will be enrolled in the EZH2 wild type cohort

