3.5.2. Rationale for Population

[figure not shown]
Preclinical studies demonstrate that B-cell lymphomas of DLBCL origin with EZH2 activating mutations are the most sensitive to GSK2816126; however, the growth of a subset of EZH2 wild-type lymphomas, SNF5-mutant malignant rhabdoid tumors, multiple myeloma, AML, neuroblastoma, prostate, breast, skin, and colon cancers are also sensitive to EZH2 inhibition. There is increasing evidence that a large number of solid tumors or subtypes may be driven by EZH2 mutation or over expression. Often, these tumors have poor prognosis. Therefore, the study includes subjects with non-Hodgkin Lymphoma and enriched for subsets (GCB-DLBCL, tFL) as well as multiple myeloma and solid tumors that have relapsed or are refractory to prior treatment with standard of care or do not have standard of care available or refuse standard of care therapy.

Part 1 will be comprised of 2 phases:

- Part 1 dose escalation which will include subjects with MM, relapsed/refractory tFL and DLBCL, other NHLs and solid tumors , and
- Part 1 cohort expansion at the highest tolerated dose/MTD which will include a cohort of subjects with relapsed/refractory GCB-DLBCL and a cohort of subjects with prostate cancer or solid tumors containing EZH2 inhibitor sensitizing mutations.

Part 2 will be comprised of cohort expansions in subjects with GCB-DLBCL, transformed follicular lymphoma and multiple myeloma.

EZH2 and H3K27me3 are dysregulated in nearly all cancers through numerous pathways including 1) recurrent gain-of-function heterozygous mutations in germinal center B-cell (GCB) DLBCL, FL, melanoma, and parathyroid adenoma, 2) EZH2 over-expression in numerous other aggressive tumors including those from prostate, breast, lung, liver, bladder, head and neck, skin, and kidney, and 3) inactivating mutations in UTX. H3K27 demethylase that acts in opposition to EZH2, described in numerous tumor types including transitional cell bladder carcinoma, esophageal squamous cell carcinoma, renal cell carcinoma, multiple myeloma, and subgroup 4 medulloblastoma [McCabe, 2014]. Furthermore, data from prostate, breast, and several other tumor types have demonstrated that increased EZH2 expression correlates with increased aggressiveness of tumors and poor prognosis [GlaxoSmithKline Document Number [2013N169204_04](#), 2017]

McCabe, 2014

Table 1. Tumor types harboring EZH2-activating mutations.

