5.2. Subject Selection Criteria

5.2.1. Part 1 Inclusion Criteria

Deviations from inclusion criteria are not allowed because they can potentially jeopardize the scientific integrity of the study, regulatory acceptability or subject safety. Therefore, adherence to the criteria as specified in the protocol is essential.

Subjects eligible for enrollment in the study must meet all of the following criteria:

1. Provided signed written informed consent.
2. Males and females ≥ 18 years of age (at the time consent is obtained).
3. Tumor type criteria

- Relapsed/refractory non-Hodgkin's lymphoma (NHL) that meets the following criteria:
 - Germinal Center B cell Diffuse large B cell lymphoma (GCB-DLBCL) relapsed or refractory to at least one prior regimen (e.g., rituximab, cyclophosphamide, doxorubicin, vincristine, prednisone [R-CHOP]) AND not a candidate for standard salvage regimens or autologous or allogeneic stem cell transplant. Local confirmation of lymphoma subtype GCB-DLBCL is allowed for enrollment but must be confirmed through central laboratory testing.
- Solid tumors that meet the following criteria:
 - Measurable disease by RECIST 1.1 in at least 1 site
 - For Castrate Resistant Prostate Cancer (CRPC) measurable disease can also include PSA level (see below)
 - Disease progression with the last line of therapy and at least one prior standard of care regimens, or tumor for which there is no approved therapy, or for which standard therapy is unsuitable or refused.
 - Mutation Status:
 - Solid tumor types, other than prostate, must have one of the following EZH2 inhibitor sensitizing mutations as determined via local testing:
 - An activating mutation in EZH2 (Y641F/C/S/H/N, A677V/G, and/or A687V)
 - Loss of a component of the SWI/SNF complex, including, but not limited to, ARID1A, SMARCB1 (aka SNF5/INI1/BAF47), SMARCA4 (aka BRG1), or PBRM1 (aka PB1) as determined by molecular testing (bi-allelic loss or mutation) or immunohistochemistry
 - Loss of BAP1 (ubiquitin carboxy-terminal hydrolase) as determined by molecular testing (bi-allelic loss or mutation) or immunohistochemistry
 - CRPC subjects:
 - Must have measurable disease by either:
 - RECIST1.1 (see [Appendix 5](#)) or,
 - A minimum PSA of 5 ng/mL
 - Disease progression on last line of therapy and must have progressed on abiraterone, enzalutamide, or taxane chemotherapy
 - Subjects may continue GnRH agonists
 - Small cell prostate cancer is eligible

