- b. For MM subjects, adequate renal function is defined as calculated creatinine clearance ≥ 30 mL/min.
- c. ECHO is the preferred method and should always be used if available

NOTE: Laboratory results obtained during Screening should be used to determine eligibility criteria. In situations where laboratory results are outside the permitted range, the investigator may opt to retest the subject and the subsequent within range screening result may be used to confirm eligibility.

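### Part 1 inclusion criterion 3 admits only GCB-DLBCL and selected solid tumors, which contradicts the planned escalation population and is carried by cross-reference into Part 2

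*Protocol*

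**What the plan says.** Section 5.2.1 of the protocol sets the Part 1 criteria as a list to be met in full: "Subjects eligible for enrollment in the study must meet all of the following criteria". It adds that "Deviations from inclusion criteria are not allowed", and section 3.2 also rules out waivers and exemptions.

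Criterion 3 of that list has two branches. The NHL branch has a single entry: "Germinal Center B cell Diffuse large B cell lymphoma (GCB-DLBCL) relapsed or refractory to at least one prior regimen", with further conditions on salvage therapy and transplant. The other branch is headed "Solid tumors that meet the following criteria" and requires a listed sensitizing mutation unless the tumor is prostate cancer. The synopsis repeats this structure.

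Section 3.5.2 describes a wider population: "Part 1 dose escalation which will include subjects with MM, relapsed/refractory tFL and DLBCL, other NHLs and solid tumors". The study design paragraph of the synopsis names the same groups. Footnote b to the organ-function table in 5.2.1 begins "For MM subjects, adequate renal function is defined as calculated creatinine clearance" and sets a separate limit for MM.

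Section 5.2.2 starts its first criterion with "In addition to inclusion criteria listed for Part 1, Part 2 will enroll" and completes the sentence by limiting Part 2 to GCB-DLBCL, tFL and MM. A bullet below it gives a prior-therapy rule for tFL and MM. Criterion 3 of 5.2.2 defines mutant and wild-type cohorts for both GCB-DLBCL and tFL.

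**The concern.** Inclusion criteria are what sites apply and monitors check. A site applying 5.2.1 as written would turn away MM, tFL, non-GCB DLBCL, other NHL and mutation-negative non-prostate solid tumors from escalation, although the synopsis and 3.5.2 place those groups there. A site following 3.5.2 would breach a criterion that cannot be waived.

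This also touches the Part 2 primary analysis. Section 3.4 includes in it GCB-DLBCL, tFL and MM patients treated at the MTD or RP2D in earlier stages, and section 12.2.2 counts MM escalation subjects at the RP2D towards the MM cohort. Whether those subjects were properly eligible therefore matters for cohorts with their own response-rate hypotheses.

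In Part 2, the cross-reference leaves unclear how much of criterion 3 carries over to tFL. The GCB-DLBCL entry excludes transplant candidates, while the tFL and MM bullet says nothing about transplant. Sites could resolve that differently within a cohort tested against a fixed 20% null.

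**Working it through.** The question is textual, so the first step sets the sections side by side.

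| Tumor type | Escalation (synopsis, 3.5.2) | Part 1 criterion 3 (5.2.1) | Part 2 cohort (5.2.2, 12.2.2) |
|---|---|---|---|
| GCB-DLBCL | yes | yes | yes, two cohorts |
| Other DLBCL | yes (DLBCL, no subtype stated) | no entry | no |
| tFL | yes | no entry | yes, two cohorts |
| Other NHL | yes | no entry | no |
| MM | yes | no entry (but renal footnote b) | yes, one cohort |
| Solid tumor with sensitizing mutation, or CRPC | yes | yes | no |
| Other solid tumor | yes (no restriction stated) | no | no |

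**Part 1.** All criteria must be met, none may be waived, and criterion 3 has no entry for four of these rows and excludes a fifth. Nothing in 5.2.1 limits criterion 3 to the expansion cohorts. The conflict with the escalation population does not depend on how 5.2.2 is read.

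**Part 2.** Taken literally, the Part 1 list plus the Part 2 list must both be met, so a tFL or MM subject fails criterion 3. The same section, however, names both diseases, gives them an entry rule and defines tFL cohorts.

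**Size.** Inputs from section 5.1: four lymphoma cohorts of up to 32 and one MM cohort of up to 40.
- Stated Part 2 maximum: 4 × 32 + 40 = 168, which reproduces.
- Stated study maximum: 40 + 27 + 15 + 168 = 250, which reproduces.
- tFL and MM places: 2 × 32 + 40 = 104; 104 / 168 = 61.9%.
- Places untouched: 2 × 32 = 64 (GCB-DLBCL).

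**Operating characteristics.** Exact binomial enumeration of the futility boundaries, subject by subject:
- Table 17 (20% against 40%, maximum 32): type I error 0.0660, power 0.8007; the protocol states 0.066 and 0.801.
- Table 18 (10% against 25%, maximum 40): type I error 0.0721, power 0.8142; the protocol states 0.072 and 0.814.

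The sample-size work is sound, so the defect is confined to the eligibility text.

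**The case against.** The strongest reply concerns Part 2. A reader might infer that three of its five cohorts have no eligible subjects and that their hypotheses would rest on ineligible patients. The documents do not support that. The sentence in 5.2.2, its bullet and the tFL cohort definitions would be pointless if criterion 3 barred tFL and MM, so the natural reading is that the Part 2 rules supply the tumor type and the other Part 1 criteria carry over. Clinical activity is analysed in everyone who received a dose (section 12.3.1), so the response-rate analyses would still run. Part 2 opens only if Part 1 supports it, and cohorts may stop from 10 (lymphoma) or 14 (MM) subjects. All of this stands. For Part 2 the fault is a loose cross-reference.

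Nor does the Part 2 sentence exclude other NHL from a planned cohort. Other NHL has no Part 2 cohort, and its conflict lies only with the escalation text.

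For Part 1, the reply is that escalation was well advanced: section 1.3.1 reports that 3000 mg exceeded the MTD and 2400 mg is the highest dose being explored. The amendment summary also says the criteria were updated to define eligibility for the Part 1 expansion. This limits the reach but does not remove the conflict. The protocol does not say escalation is closed, lets dose levels be expanded up to 12 subjects, and keeps the wider population in its current synopsis and 3.5.2.

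**Conclusion.** The point holds as an internal contradiction. For Part 1 it is unconditional: a mandatory, non-waivable criterion excludes tumor types that the protocol says escalation enrols, and the MM footnote sits inside criteria that admit no MM subject. That criterion 3 was drafted for the expansion cohorts is an inference from its content and from the amendment summary. The number of escalation subjects still to be enrolled is not given, so the Part 1 effect cannot be sized and could be small.

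For Part 2 the figure of 104 of 168 (62%) is a ceiling. It assumes the literal reading, every cohort filled to its maximum, and Part 2 opening. The evident intent is that tFL and MM are eligible. No sample size, boundary or error rate is affected.

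**What to change.** Reconcile 5.2.1, 5.2.2, 3.5.2 and the synopsis.

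1. In 5.2.1 and the synopsis, state criterion 3 separately for dose escalation and for Part 1 expansion. The present GCB-DLBCL and solid-tumor text can serve the expansion. The sponsor should confirm which tumor types, and which prior-therapy, measurability and mutation conditions, apply to any remaining escalation subjects. If the narrower population is intended, amend the synopsis and 3.5.2 to match.
2. In 5.2.2 and the synopsis, say that Part 1 criteria 1, 2 and 4 to 9 carry over, that the Part 2 tumor-type rules replace criterion 3 for tFL and MM, and that GCB-DLBCL keeps its criterion 3 entry. The MM renal footnote belongs to criterion 9 and so carries over.

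The cost is amendment wording plus one sponsor decision on the escalation population. The clarification itself adds no subjects or procedures and requires no change to the statistical design.

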5.2.3. Part 1 and 2 Exclusion Criteria

Deviations from exclusion criteria are not allowed because they can potentially jeopardize the scientific integrity of the study, regulatory acceptability or subject safety. Therefore, adherence to the criteria as specified in the protocol is essential.

Subjects meeting any of the following criteria must not be enrolled in the study:

1. Receiving any cancer therapy within 2 weeks of first dose (including surgery and/or tumor embolization)

Note: the following are allowed:

- Corticosteroids to control systemic or local symptoms, up to a dose of 10 mg prednisone or equivalent daily and stable for at least 7 days **prior** to enrollment.
- Subjects with prostate cancer may remain on GnRH agonists. Other hormonal therapies (e.g., bicalutamide, abiraterone and enzlutamide) for prostate cancer must be stopped 4 weeks prior to enrolment.

Note: the following are NOT allowed:

- Chemotherapy regimens with delayed toxicity within the last 3 weeks.
 - Nitrogen mustards, Melphalan, Monoclonal antibody or Nitrosourea within the last 6 weeks.
2. Any major surgery, radiotherapy or immunotherapy within the 4 weeks prior to first dose of study drug, or palliative radiotherapy to a single symptomatic lesion within the 2 weeks prior to first dose of study drugs.
 3. Subjects with prior allogeneic transplant are excluded: however, subjects who have previously received an autologous stem cell transplant are allowed if a minimum of 100 days has elapsed from the time of transplant and the subject has recovered from transplant-associated toxicities prior to the first dose of GSK2816126
 4. Received an investigational anti-cancer drug within 6 weeks, or within 5 half-lives (whichever is shorter) of the first dose of study drug. A minimum of 14 days must have passed between the last dose of prior investigational agent and the first dose of study drug.
 5. Current use of a prohibited medication or expected to require any of these medications during treatment with study drugs (see Section 9).
 6. Known human immunodeficiency virus (HIV), or serological evidence for Hepatitis B (positive HBsAg) or chronic Hepatitis C infection.
 - Subjects who are negative for HBsAg, but HBcAb positive, a HBV DNA (viral load) test will be performed and if negative are eligible.

- Subjects with positive Hepatitis C antibody serology with a negative HCV RNA test results are eligible.
7. Concurrent use of therapeutic warfin is allowed. However, anticoagulants that do not have reversal agents available are prohibited (see Section 9.2). .
8. Unresolved toxicity greater than Grade 1 National Cancer Institute – Common Terminology Criteria for Adverse Events (NCI-CTCAE) version 4 from previous anti-cancer therapy, with the exception of alopecia and peripheral neuropathy [NCI-CTCAE, 2009].
- Lymphoma subjects with \leq Grade 3 lymphopenia can be enrolled at the discretion of the investigator
9. Packed red blood cell or platelet transfusion within 7 days of screening laboratory tests.
10. Psychological, familial, sociological or geographical conditions that do not permit compliance with the protocol.
11. Cardiac exclusion criteria:
- History of acute coronary syndromes (including myocardial infarction and unstable angina), coronary angioplasty, or stenting within the past 6 months prior to first dose of study drug.
 - QTcF interval >450 msec
 - Uncontrolled arrhythmias. Subjects with rate controlled atrial fibrillation for >1 month prior to first dose of study drugs may be eligible.
 - Class II, III or IV heart failure as defined by the New York Heart Association (NYHA) functional classification system.
12. Known immediate or delayed hypersensitivity reaction or idiosyncrasy to drugs chemically related to the study drug or their excipients.
13. Pregnant or lactating female.
14. Unwillingness or inability to follow the procedures outlined in the protocol.
15. Uncontrolled diabetes or other medical condition that may interfere with assessment of toxicity.
16. Central nervous system (CNS) metastases, with the following exception:
- Subjects who have previously treated CNS metastases, are asymptomatic, and have no requirement for steroids at least 14 days prior to first dose of study drug.
 - Subjects with carcinomatous meningitis are excluded regardless of clinical stability.
17. Invasive malignancy or history of invasive malignancy other than disease under study, except as noted below:
- Any other invasive malignancy from which the subject has been disease-free for more than 2 years and, in the opinion of the principal investigator and GSK Medical Monitor, will not affect the evaluation of the effects of

this clinical trial treatment on currently targeted malignancy, can be included in this clinical trial.

- Curatively treated non-melanoma skin cancer and any carcinoma-in-situ.

6. COMPLETION OR WITHDRAWAL OF SUBJECTS

6.1. Screen and Baseline Failures

Data for screen and baseline failures will be collected in source documentation at the site but will not be transmitted to GSK.

Retention of screen-failure tumor tissue: all or a portion of archival or fresh biopsy tissue from screen-failure subjects, used for central testing of GCB-DLBCL or EZH2 mutation status, will be retained. This tissue may be used in the validation of potential diagnostic assays to detect EZH2 mutations and/or for GCB-DLBCL subtyping.

6.2. Subject Completion Criteria

For Part 1 (dose-escalation phase), a completed subject is one who has completed the DLT observation period, has discontinued study treatment for reasons listed in Section [6.3](#) and completed a post-treatment follow-up visit or has died while receiving study treatment or are receiving ongoing study treatment at the time of the Sponsor's decision to close the study.

For Part 2 (expansion cohort), a completed subject is one who has discontinued study treatment for reasons listed in Section [6.3](#) and completed a post-treatment follow-up visit or has died while receiving study treatment.

6.3. Permanent Discontinuation from Study Treatment

Subjects will receive study treatment until disease progression, death or unacceptable toxicity, including meeting stopping criteria for liver chemistry defined in Section [8.3.1](#). In addition, study treatment will be permanently discontinued for any of the following reasons:

- Substantial deviation(s) from the protocol
- Request of the subject or proxy (withdrawal of consent by subject or proxy)
- Investigator's discretion
- A dose delay of >21days unless the investigator and GSK Medical Monitor agree that further treatment may benefit the subject
- Intercurrent illness that prevents further administration of study treatment(s)
- Subject is lost to follow-up
- Study is closed or terminated
- Female subject who becomes pregnant while on study treatment

The primary reason study treatment was permanently discontinued must be documented in the subject's medical records and eCRF.

If the subject voluntarily discontinues from treatment due to toxicity, 'adverse event' will be recorded as the primary reason for permanently discontinuation on the eCRF.

Once a subject has permanently discontinued from study treatment, the subject will not be allowed to be retreated.

All subjects who discontinue from study treatment will have safety/disease assessments at the post study treatment Follow Up Visit as specified in the Time and Events Tables.

6.4. Study Completion

A subject will be considered to have completed the study after they have completed their post treatment follow up visit or if the subject dies or is still in follow-up at the time the study is closed or terminated, whichever is sooner. Document the cause of death in the CRF. A subject will be considered to have withdrawn from the study if the subject has not died and is lost to follow-up, has withdrawn consent, or at the investigator's discretion is no longer being followed.

Per the EU Clinical Trial Directive, the end of the study is defined as the last subject's last visit.

6.5. Treatment after the End of the Study

The investigator is responsible for ensuring that consideration has been given for the post-study care of the subject's medical condition whether or not GSK is providing specific post-study treatment.

7. STUDY ASSESSMENTS AND PROCEDURES

A signed, written informed consent form must be obtained from the subject prior to any study-specific procedures or assessments being performed.

The timing of each assessment is listed in the Time and Events Table (Section 7.1). The timing and number of the planned study assessments may be altered during the course of the study based on newly available data (e.g. to obtain data closer to the time of peak plasma concentrations) to ensure appropriate monitoring for the following assessments: safety, PK, PD/biomarker. The change in timing or addition of time points for any of the planned study assessments listed above must be approved and documented by GSK, but this will not constitute a protocol amendment. The institutional review board (IRB) or ethics committee (EC) will be informed of any safety issues that require alteration of the safety monitoring scheme.

Whenever vital signs, 12-lead ECGs and blood draws are scheduled for the same nominal time, the assessments should occur in the following order: 12-lead ECG, vital signs, blood draws. Detailed procedures for obtaining each assessment are provided in the SPM.

